2.4.4.3 Multiplicity issues

No adjustments for multiplicity will be applied for this study due to the small sample size and the fact that many patients will not have the opportunity to complete the planned 52-week treatment period. All reported p-values will be nominal.

2.4.5 Analyses of safety data

The summary of safety results will be presented by treatment groups.

General common rules

All safety analyses will be performed on the safety population as defined in [Section 2.3.2](#), unless otherwise specified, using the following common rules:

- Safety data in patients who do not belong to the safety population (eg, exposed but not randomized) will be listed separately
- The baseline value is defined as the last available value prior to the first dose of study medication.
- The potentially clinically significant abnormality (PCSA) values are defined as abnormal values considered medically important by the Sponsor according to predefined criteria/thresholds based on literature review and defined by the Sponsor for clinical laboratory tests, vital signs, and ECG (PCSA in BTD-009536 version 3, see [Appendix B](#))
- PCSA criteria will determine which patients had at least 1 PCSA during the TEAE period, taking into account all evaluations performed during the TEAE period, including nonscheduled or repeated evaluations. The number of all such patients will be the numerator for the on-treatment PCSA percentage
- The treatment-emergent PCSA denominator by group for a given parameter will be based on the number of patients assessed for that given parameter in the treatment-emergent adverse event period by treatment group on the safety population.
- For quantitative safety parameters based on central laboratory/reading measurements, descriptive statistics will be used to summarize results and change from baseline values by visit and treatment group. Summaries will include the endpoint value. The endpoint value is commonly defined as the value collected at the same day/time of the last dose of investigational product. If this value is missing, this endpoint value will be the closest one prior to the last dose intake.
- Analyses of the safety variables will be essentially descriptive and no systematic testing is planned.

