11.4.3 Analyses of safety data

The summary of safety results will be presented by treatment group. Incidence rates and exposure adjusted event summaries will be provided for categorical safety summaries.

All safety analyses will be performed on the safety population using the following common rules:

The baseline value is defined generally as the last available value before randomization.

- The observation period to be used for the safety population is the TEAE period. The TEAE period is defined as the time from first dose of randomized study treatment to the last dose date of IMP + 60 days.
- For quantitative safety parameters based on central laboratory/reading measurements, descriptive statistics will be used to summarize results and change from baseline values by visit and treatment group.
- The analysis of the safety variables will be essentially descriptive and no hypothesis testing is planned.

The following definitions will be applied to laboratory parameters, vital signs and ECG.

- The potentially clinically significant abnormality (PCSA) values are defined as abnormal values considered medically important by the Sponsor according to predefined

criteria/thresholds based on literature review and defined by the Sponsor for clinical laboratory tests, vital signs, and ECG.

- PCSA criteria will determine which patients had at least 1 PCSA during the on-treatment period, taking into account all evaluations performed during the on-treatment period, including unscheduled or repeated evaluations. The number of all such patients will be the numerator for the on-treatment PCSA percentage.

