1.3 DETERMINATION OF SAMPLE SIZE

The sample size calculations are based on the primary efficacy variable of sustained remission at Week 52. Data from another trial that evaluated the safety and efficacy of tocilizumab in a similar population show that the expected event rate in Group C (placebo with 26-week taper, n = 60) is 14% and in Group D (placebo with 52-week taper, n = 120) is 18% (1). Assuming a treatment difference of 40% and a significance level of 0.01 (2-sided) this will ensure that all comparisons of the primary endpoint in Group A (sarilumab 200 mg, n = 120) and Group B (sarilumab 150 mg, n = 60) compared to the 2 control groups will have at least 90% power. The sample size has also been selected to ensure adequate power for sensitivity analyses excluding acute phase reactants from the primary endpoint definition.

The above calculations were for the full enrollment. However, the number of randomized patients is 83 in 4 arms at the time of the premature termination of the study. In addition, based on patients' enrollment dates and the study discontinuation plan, only about 36 patients (out of 83) had an opportunity to complete the 52-week treatment period. For the cohort of patients who did not have an opportunity to complete the 52-week treatment period, it is not meaningful to define the endpoint of sustained remission at Week 52. Therefore, the analysis of primary endpoint will be limited to the cohort of patients who had an opportunity to complete the 52-week treatment period. Due to the small number of patients (n=36) in this cohort (see Section 2.3.1 for definition of the cohort), the powers on the primary endpoint are minimal. As a result, all the efficacy analyses will be descriptive in nature and all reported p-values will be nominal for the study.

Based on patients' enrollment dates, all enrolled patients (n=83) had an opportunity to complete at least 24 weeks of treatment, therefore, an additional endpoint, sustained remission at Week 24 is added in the SAP (see Section 2.1.3.1 for the detail definition). Table 1 provides the power calculations on the additional endpoint of sustained remission at Week 24. Due to the small number of patients in each individual treatment group, the power calculations were also provided for the comparison between the combined sarilumab groups (i.e., Group A+B) and the combined placebo groups (i.e., Group C+D) assuming the same effect sizes as mentioned above.

Table 1: Updated power calculations

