1.6 STATISTICAL MODIFICATIONS MADE IN THE STATISTICAL ANALYSIS PLAN

Due to the early termination of the study and study discontinuation plan, a large amount of data will not be able to be collected since many enrolled patients will not complete all planned study visits and study procedures for the assessments of efficacy, ADA, and biomarker endpoints. In addition, the number of randomized patients is 83 in 4 arms (out of 360 planned) at the time of the premature termination of the study. The changes from the statistical analysis plan outlined in the protocol are summarized below.

- The primary endpoint for the study is sustained remission at Week 52. Based on patients' enrollment dates and the study discontinuation plan, only about 36 patients (out of 83) had an opportunity to complete the 52-week treatment period. For the cohort of patients who

did not have an opportunity to complete the 52-week treatment period, it is not meaningful to define the endpoint of sustained remission at Week 52. Therefore, the analysis of primary endpoint will be limited to the cohort of patients who had an opportunity to complete the 52-week treatment period. Details can be found in [Section 2.1.3.1](#) and [Section 2.4.4.1](#).

- Based on patients' enrollment dates and the study discontinuation plan, all patients should have had the opportunity to be treated for at least 24 weeks, so an additional endpoint, sustained remission at Week 24, is added in the SAP. Details can be found in [Section 2.1.3.1](#).
- Due to the same reason as mentioned above, the secondary endpoints of cumulative GTI scores at Week 52 will be limited to the cohort of patients who had an opportunity to complete the 52-week treatment period. In addition, the cumulative GTI scores will also be assessed at Week 24. Details are provided in [Section 2.1.3.2](#).
- The missing data imputation strategy for defining the endpoints of sustained remission at W24 and W52, and cumulative GTI scores at W24 and W52 can be found in [Section 2.1.3.1](#) and [Section 2.1.3.2](#), respectively; the rest of efficacy analyses will be based on data as observed, no missing data will be imputed.

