2.4.3.1 Extent of investigational medicinal product exposure

The extent of SC IMP exposure will be assessed by the duration of SC IMP exposure and actual dose information.

The duration of SC IMP exposure is defined as last DB dose date – first DB dose date +14 days, regardless of unplanned intermittent discontinuations (see [Section 2.5.3](#) for calculation in case of missing or incomplete data).

Duration of SC IMP exposure will be summarized descriptively as a quantitative variable (number, mean, SD, median, minimum, and maximum). In addition, duration of treatment exposure will also be summarized categorically by numbers and percentages for each of the following categories and cumulatively according to these categories: ≤ 4 weeks, >4 and ≤ 8 weeks, >8 and ≤ 12 weeks, >12 and ≤ 16 weeks, >16 and ≤ 20 weeks, >20 and ≤ 24 weeks, >24 and ≤ 32 weeks, >32 and ≤ 40 weeks, >40 and ≤ 52 weeks and >52 weeks.

Additionally, the cumulative duration of treatment exposure, defined as the sum of patients' duration of treatment exposure and expressed in patient years, will be provided.

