2.4.5.1 Analyses of adverse events

Generalities

The primary focus of AE reporting will be on TEAEs. Pre-treatment and post-treatment AEs will be described separately.

If an AE date/time of onset (occurrence, worsening, or becoming serious) is incomplete, an imputation algorithm will be used to classify the AE as pre-treatment, or TEAE, or post-treatment AE. The algorithm for imputing date/time of onset will be conservative and will classify an AE as treatment-emergent unless there is definitive information to determine it is pre-treatment or post-treatment. Details on classification of AEs with missing or partial onset dates are provided in [Section 2.5.3](#).

Adverse event incidence tables will present by SOC, HLGT, HLT, and PT, sorted in SOC internationally agreed order and then alphabetical order, and present the number (n) and percentage (%) of patients experiencing an AE by treatment group. Multiple occurrences of the same event in the same patient will be counted only once in the tables within a treatment phase. The denominator for computation of percentages is the safety population within each treatment group.

The tables by primary SOC and PT will be sorted by internationally agreed order of SOC and decreasing frequency of PT within SOC. Sorting will be based on results for the sarilumab 200mg arm.

Analysis of all treatment-emergent adverse events

The following TEAE summaries will be generated for the safety population.

- Overview of TEAEs, summarizing number (%) of patients with any
 - TEAE
 - Serious TEAE
 - TEAE leading to death
 - TEAE leading to permanent treatment discontinuation
- All TEAEs by primary SOC, HLGT, HLT, and PT, showing number (%) of patients with at least one TEAE sorted by SOC internationally agreed order. The other level (HLGT, HLT, PT) will be presented in an alphabetic order.
- All TEAEs by primary SOC and PT, showing number (%) of patients with at least one TEAE, sorted by SOC internationally agreed order and decreasing incidence of PTs within SOC. This sorting order will be applied to all other tables, unless otherwise specified.
- All TEAEs by primary SOC, showing number (%) of patients with at least one TEAE, sorted by internationally agreed order of primary SOC.

- All TEAEs by relationship, presented by primary SOC, HLG, HLT, and PT, showing number (%) of patients with at least one TEAE, sorted by SOC internationally agreed order. The other level (HLG, HLT, PT) will be presented in an alphabetic order.

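### The SAP drops the protocol's exposure-adjusted safety summaries without saying so, although early termination leaves potential treatment time ranging from about 24 to 52 weeks

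*SAP*

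**What the plan says.** Protocol 11.4.3 asks for safety results by treatment group and then states: "Incidence rates and exposure adjusted event summaries will be provided for categorical safety summaries".

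SAP 2.4.5 opens with the first of these two statements, "The summary of safety results will be presented by treatment groups", and goes straight on to its common rules. SAP 2.4.5.1 says that the AE tables will "present the number (n) and percentage (%) of patients experiencing an AE by treatment group", and adds: "The denominator for computation of percentages is the safety population within each treatment group". SAP 2.4.5.2 gives deaths as number (%). No event rate per unit of patient-time is specified in SAP 2.4.5.1 to 2.4.5.4 or in Appendix C.

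SAP 1.6 introduces its list of departures with "The changes from the statistical analysis plan outlined in the protocol are summarized below". The items cover the efficacy endpoints and their populations, imputation, significance level, multiplicity and subgroups. The loss of the exposure-adjusted summaries is not among them.

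On follow-up, SAP 1.3 says that "all enrolled patients (n=83) had an opportunity to complete at least 24 weeks of treatment", but that "only about 36 patients (out of 83) had an opportunity to complete the 52-week treatment period".

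The SAP keeps some related material. Section 2.4.3.1 reports cumulative exposure, which "expressed in patient years, will be provided". Each AESI category in 2.4.5.1 gets a treatment duration summary and incidence by patient and by event. Section 2.4.5.3 keeps Kaplan-Meier time to onset for selected laboratory abnormalities and allows, without committing to it, a display of abnormal liver tests by duration of exposure.

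**The concern.** When every patient is to be treated for 52 weeks, a percentage of patients with an event has an implied time base. Termination removes it: 47 of 83 patients (57%) could not reach Week 52, and early stoppers contribute less still. SAP 1.3 accepts this reasoning for efficacy, where it restricts the Week 52 endpoint to patients who could have reached Week 52. The safety section has no counterpart, and the one protocol sentence that would have dealt with the problem is the one that disappeared.

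Two things are at stake. First, a percentage for TEAEs, SAEs, discontinuations or deaths cannot be read as a 52-week risk, or as the risk over any stated period. Second, if discontinuation differs between arms, the planned tables give no means of adjusting for it. There is also a traceability problem, because a protocol commitment is dropped without being recorded.

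**Working it through.** **1. Potential treatment time, from the plan's own dates.** Inputs: recruitment suspended 19 March 2020 (SAP 1); screening of up to 42 days (Protocol 1.2); latest end-of-treatment visit 13 October 2020 (SAP 1.1); Week 52 set randomized before 16 October 2019 (SAP 2.3.1).

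- Randomized on 16 October 2019: 363 days / 7 = 51.9 weeks.
- Randomized on 19 March 2020: 208 / 7 = 29.7 weeks.
- Randomized 42 days after the suspension, if a patient already in screening went on: 166 / 7 = 23.7 weeks.

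This reproduces the SAP's span of about 24 to 52 weeks. It is opportunity, not observed exposure; the exposure categories in SAP 2.4.3.1 start at 4 weeks or less.

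**2. Group sizes.** 83 split 2:1:1:2 gives 27.7 / 13.8 / 13.8 / 27.7, in line with the estimated 28 / 14 / 14 / 27 in SAP Table 1.

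**3. Person-time if nobody stops early.** Patient-years = (36 × 52 + 47 × m) / 52, where m is the assumed mean number of weeks for the other 47.

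| m (weeks) | Total patient-years | Per 14 patients (total × 14/83) |
|---|---|---|
| 24 | 57.7 | 9.7 |
| 30 | 63.1 | 10.6 |
| 38 | 70.3 | 11.9 |
| 52 (as planned) | 83.0 | 14.0 |

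**4. Effect of observation time on a crude percentage.** Under an assumed constant hazard, expected percentage = 100 × (1 − exp(−rate × weeks/52)).

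| Assumed rate per patient-year | 24 weeks | 52 weeks |
|---|---|---|
| 0.3 | 12.9% | 25.9% |
| 0.5 | 20.6% | 39.3% |
| 1.0 | 37.0% | 63.2% |

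This contrast is between patients with different follow-up. It is not an expected difference between arms.

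**5. Chance imbalance between arms.** Protocol 8.4 specifies blocked randomization within two prednisone strata, each patient taking the next entry. Potential exposure depends on randomization date, which blocking tends to balance. I simulated 83 patients in order of enrolment: 36 at 52 weeks and 47 uniform over 24 to 52 (overall mean 44.1 weeks). Block size and stratum split are not given, so I assumed blocks of 6 or 12 and two equal strata. The 95% limits for a difference in mean potential exposure run from about ±2.3 weeks (28 versus 14 patients, blocks of 6) to about ±3.6 weeks (14 versus 14, blocks of 12).

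At 0.5 per patient-year, a 3.6-week gap centred on 44.1 weeks moves the expected percentage by exp(−0.5 × 42.3/52) − exp(−0.5 × 45.9/52) = 0.666 − 0.643, about 2.3 points. One patient in 14 is 7.1 points.

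**6. What the restored summary would look like.** Two patients with an event among 14 is 14.3% (exact 95% CI 1.8 to 42.8). Two first events in an assumed 10.7 patient-years is 18.7 per 100 patient-years (exact Poisson 95% CI 2.3 to 67.5, from chi-square(0.025; 4)/2 and chi-square(0.975; 6)/2 divided by 10.7). The rate supplies a time base; it does not add precision.

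**The case against.** The strongest reply is that this is a terminated, descriptive study with no safety testing, and that the SAP has not abandoned exposure. It reports patient-years, gives duration and event incidence for each AESI category, and keeps Kaplan-Meier for several laboratory events. The protocol defines no estimator, and its own AE section (11.4.3.1) is written in n (%). All of that is true, and it limits the point. None of it supplies an event rate for TEAEs, SAEs, discontinuations or deaths, and none of it explains why the protocol sentence went.

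Some stronger readings are tempting but are not supported:

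- **Built-in bias.** A reader might infer that the percentages systematically favour one arm. SAP 1 says that termination was unrelated to safety issues, and it applied to all arms under randomized allocation, so potential exposure is balanced in expectation and nearly so by chance (step 5). No arm should average close to 52 weeks when 47 of 83 patients could not reach it.
- **Rescue shortens exposure.** Patients on corticosteroid rescue are to continue the injections (Protocol 8.2; SAP 2.1.2), and the TEAE period is defined by injection dates (SAP 2.1.4). Rescue with corticosteroids does not of itself shorten time at risk; only a move to other agents requires stopping study treatment (Protocol 6.1).
- **Safety arms should be pooled as for efficacy.** The protocol also asks for safety by treatment group. Pooling Groups C and D would mix 26- and 52-week steroid tapers, so pooled columns are a debatable preference and not part of this point.

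**Conclusion.** The point holds as an unlisted departure from the protocol, with a practical consequence of modest size. As written, the TEAE, SAE, discontinuation and death tables will give percentages that refer to no defined period, when individual potential treatment time varies by a factor of about two. For a given event rate, that variation alone can nearly double the expected percentage (20.6% against 39.3% at 0.5 per patient-year).

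The consequence is mainly for absolute risk and for adjusting for any differential discontinuation, which the documents neither show nor exclude. The chance effect on comparisons between arms is small beside the imprecision of groups of about 14, which exposure adjustment does not cure.

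The figures assume a constant hazard, the mixture and blocking in step 5, and the SAP's estimated group sizes. If events cluster early in treatment, the gap in step 4 would be smaller, which is a reason to show the rate beside the percentage and not in place of it.

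**What to change.** In SAP 2.4.5 and 2.4.5.1, restore the protocol sentence and define the summary. Beside n (%), report by treatment group the number of patients with a first event per 100 patient-years at risk over the TEAE period, with an exact 95% CI, for:

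- any TEAE;
- any SAE;
- each AESI category;
- any TEAE leading to treatment discontinuation;
- any TEAE leading to death.

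If the sponsor prefers not to restore it, the omission should be listed and justified in SAP 1.6.

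The cost is SAP wording, extra table columns and one derivation, with no new data. The patient-years in SAP 2.4.3.1 cannot serve as the denominator, because they measure treatment duration (last dose minus first dose plus 14 days). Time at risk has to be computed separately for each category, from first dose to the first event or, if there is none, to the earlier of last dose plus 60 days and end of observation. End of observation matters because the discontinuation plan sets the final visit 6 weeks (42 days) after treatment stops, which can fall before day 60.

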
ASSESSMENT SCHEDULE
	
The study will consist of the following visits:
 
 • Visit 1 (D -42 - D -1): Screening • Visit 2 (D1): Baseline, randomization, first study drug administration • Visit 2 to 12 (D1-Week 52): on treatment (double-blind phase) • Visit 12 (Week 52): End of Treatment (EOT) visit (last sarilumab or matching placebo administration at Week 50) • Visit 13 (Week 58): 6 weeks post-treatment follow up visit • Visit 14 (Week 76): EOS visit 
Patient's CS tapering period may vary (maximum of 52 weeks) depending on the dose of daily prednisone at the time of randomization.
 
At screening and baseline visits, a physical examination to assess disease activity and general health will be performed. Patients will be assessed for active or latent tuberculosis (TB) at baseline and during the study. Laboratory tests includes hematology, chemistry, lipids, glucose, insulin, antinuclear antibodies (ANA), glycosylated hemoglobin A1c (HbA1c), urinalysis, human immunodeficiency virus (HIV), Hepatitis B and C, serum and plasma for biomarkers and a 12-lead electrocardiogram (ECG). A serum pregnancy test for women of child bearing potential (WOCBP) will be obtained at screening as well.
 
Blood samples for circulating proteins (serum and plasma) and for deoxyribonucleic acid (DNA) and ribonucleic acid (RNA) will be collected from each consenting patient, by signing off the additional research program part (optional) included in the main informed consent forms.
 
Safety assessments are done at each study visit and include AEs, serious adverse events (SAEs) and adverse events of special interest (AESIs) including but not limited to neutropenia, thrombocytopenia, elevations in hepatic enzymes leading to permanent discontinuation and TB, and potential opportunistic infections.
 
A dual assessor approach will be required in order to maintain the blind during the double-blind treatment period with sarilumab, placebo, and prednisone. Efficacy Assessor should be a rheumatologist or other skilled GCA assessor and may be the Principal Investigator; they will be responsible for completing the overall evaluation and management of GCA disease activity. The Safety Assessor should be a physician; they will be responsible for assessing and managing any safety concerns of the patient during the course of the study including access to the patient's laboratory data and AEs, performing assessments related to GTI. The

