2.1.4.3 Laboratory safety variables

Clinical laboratory data will include hematology, clinical chemistry, and urinalysis. Clinical laboratory values will be converted to standard international units; international units will be used in all listings and tables. In addition, the lipids parameters will also be summarized in US units.

Hematology and chemistry data will be collected at screening, baseline, Weeks 4,12, 24, 40, and 52, and/or early termination unless otherwise specified. The laboratory parameters will be classified as follows:

- Hematology
 - **Red blood cells and platelets and coagulation:** hemoglobin, hematocrit, platelet count, red blood cell (RBC) count, and RBC morphology (if RBC count is abnormal).
 - **White blood cells:** white blood cell (WBC) count and WBC differential (neutrophils, lymphocytes, monocytes, basophils, eosinophils).
- Clinical chemistry
 - **Metabolism:** fasting lipids (total cholesterol, high density lipoprotein cholesterol (HDL-C), low density lipoprotein cholesterol (LDL-C), ratio of HDL-C versus LDL-C (HDL-C:LDL-C), triglycerides), total proteins, CRP, fasting glucose, and hemoglobin A1c (HbA1c).

- **Electrolytes:** sodium, potassium, chloride, calcium, phosphate, and bicarbonate.
- **Renal function:** creatinine, creatinine clearance, uric acid, and blood urea nitrogen (BUN).
- **Liver function:** alanine aminotransferase (ALT)/SGPT, aspartate aminotransferase (AST)/SGOT, alkaline phosphatase (ALP), albumin, total bilirubin, conjugated and unconjugated bilirubin, and lactate dehydrogenase (LDH).
- **Pregnancy test:** Serum β -hCG for all women of childbearing potential (screening only).
- **TB screen:** QuantiFERON®-TB Gold evaluation.
- **Hepatitis screen:** Hepatitis B and C serology, human immunodeficiency virus serology.

Urine samples will be collected as follows:

- **Urinalysis - dipstick:** pH, specific gravity, blood, glucose, protein, nitrates, leukocyte esterase, and bilirubin. If any parameter on the dipstick is abnormal, a urine sample was to be sent to the central laboratory for testing.

A urine pregnancy test was done for all women of childbearing potential at baseline, all visits up to Week 52 or early termination.

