2.4.5.4 Analyses of vital sign variables

The summary statistics (including number, mean, median, SD, minimum, and maximum) of all vital signs variables (vital signs values and changes from baseline) will be calculated for each visit or study assessment (baseline, each post baseline time point, endpoint) by treatment group.

The incidence of PCSAs at any time during the TEAE period will be summarized by treatment group whatever the baseline level and/or according to the following baseline status categories:

- Normal/Missing
- Abnormal according to PCSA criterion or criteria

Listings will be provided with flags indicating the PCSA values.

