2.5.4 Windows for time points

Visit windows based on days relative to the first IMP dose will be used to map the efficacy, lab, vital signs, PK and ADA measurements to each scheduled visit (see [Appendix H](#)). The following rule will be applied when mapping the measurements to the visit:

- For the same parameter (i.e., efficacy, lab, or vital signs), if a patient has more than one measurement at different dates within the same visit window, the scheduled measurement that is closest to the target date will be used (in case of tie select the latest). If there is no scheduled measurement within the visit window, the unscheduled measurement that is closest to the target date will be used (in case of tie select the latest).
- When a patient has more than one measurement on the same parameter on the same date, then the one with the later/largest sample ID will be used.
- If there is no measurement for a given parameter in an analysis window, data will be considered missing for the corresponding visit.

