HbA1c	X			X		X			X		X	X		
CRP ^l	X	X	X	X	X	X	X	X	X	X	X	X		
ESR ^l	X	X	X	X	X	X	X	X	X	X	X	X		
Urinalysis ^m	X													
Virology ⁿ	X													
Serum pregnancy test ^o	X													
Urine pregnancy test ^o		X		X	X	X	X	X	X	X	X	X		
12-lead ECG	X													
Serum sarilumab ^j		X	X	X		X	X		X ^p			X	X	
Anti-drug antibody ^j		X				X			X			X	X	
Genotyping and biomarkers ^j														
Biomarkers-IL-6 and sIL-6R		X	X			X			X			X		
Blood for circulating immune cell phenotyping ^q		X		X					X					
Future Use of Samples for Circulating proteins (serum/plasma) ^r (optional)		X	X			X			X			X		

VISIT	V1	V2	V3	V4	V5	V6	V7	V8	V9	V10	V11	V12 (EOT)	V13	V14 (EOS)
DAY	D -42 to D -1	D1	D15 (±3)	D29 (±3)	D57 (±3)	D85 (±3)	D113 (±3)	D141 (±3)	D169 (±3)	D225 (±3)	D281 (±3)	D365 (±3)	D407 (±3)	D532 (±3)
WEEK		Wk 0	Wk 2	Wk 4	Wk 8	Wk 12	Wk 16	Wk 20	Wk 24	Wk 32	Wk 40	Wk 52	Wk 58	Wk 76
DNA ^S (optional)		X												
RNA ^S (optional)		X	X											

AE = Adverse event; ANA = Antinuclear antibodies; CRP = C-reactive protein; D = Day; DNA = Deoxyribonucleic acid; ECG = Electrocardiogram; EOT = End of treatment; EOS = End of study; EQ-5D-3L = EuroQol five-dimensional three-level questionnaire; ESR = Erythrocyte sedimentation rate; FACIT-Fatigue = Functional assessment of chronic illness therapy fatigue scale; GCA = Giant cell arteritis; GTI = Glucocorticoid toxicity index; HAQ-DI = Health assessment questionnaire disability index; HbA1c = Hemoglobin A1c; HBsAg = Hepatitis B surface antigen; HBcore Ab = Hepatitis B core antibodies; HCV = Hepatitis C virus; IL = Interleukin; IMP = Investigational medicinal product; IRT = Interactive response technology; MD-VAS = Physician global assessment of disease activity- visual analog scale; MRI = Magnetic resonance imaging; Pain VAS = Pain visual analog scale; PROs = Patient reported outcomes; Pt-VAS = Patient global assessment of disease activity – visual analog scale; RNA = Ribonucleic acid; SAE = Serious adverse event; SF-36v2 = Short form 36 version 2; TB = Tuberculosis; V = Visit; Wk = Week.

- a If ultrasound is being used as a diagnostic tool of GCA, the image needs to be submitted to the central reader for confirmation of eligibility.
- b Targeted physical examination: head, eyes, ears, neck and throat, skin, respiratory, cardiovascular, neurologic, lymphatic examinations and abdominal examination.
- c Last administration of sarilumab is at Week 50.

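### SAP 2.4.5 stops the endpoint value at the last dose: read as the SC dose, a completer's laboratory endpoint falls back from Week 52 to Week 40 unless an unscheduled sample intervenes

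*SAP*

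**What the plan says.** SAP 2.4.5 (general common rules) introduces the rule for central laboratory or central reading data: "For quantitative safety parameters based on central laboratory/reading measurements, descriptive statistics will be used". It then says: "The endpoint value is commonly defined as the value collected at the same day/time of the last dose of investigational product". The fallback is: "If this value is missing, this endpoint value will be the closest one prior to the last dose intake". Nothing in the rule admits a value after the last dose.

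SAP 2.4.5.3 requests an endpoint summary for all laboratory variables. SAP 2.4.5.4 requests one for vital signs too, "for each visit or study assessment (baseline, each post baseline time point, endpoint) by treatment group", without defining it.

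The schedule is as follows:

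- SAP Appendix A, footnote c: "Last administration of sarilumab is at Week 50". The Protocol summary (assessment schedule) agrees: "Visit 12 (Week 52): End of Treatment (EOT) visit (last sarilumab or matching placebo administration at Week 50".
- SAP 2.1.4.3: "Hematology and chemistry data will be collected at screening, baseline, Weeks 4,12, 24, 40, and 52", or at early termination.
- In the flow chart, Week 40 (Day 281) is followed directly by Week 52 (Day 365). Hematology, chemistry, lipids, glucose, HbA1c, CRP and vital signs are due at both. No hematology or chemistry is scheduled after EOT.

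For by-visit tables, SAP 2.5.4 says that when several values share a window, "the scheduled measurement that is closest to the target date will be used".

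**The concern.** The rule presupposes a safety sample on the day of the last dose. This trial's schedule does not provide one: the last injection falls between visits, and the EOT sample follows it. The endpoint row is the one by-treatment laboratory summary that puts completers and early stoppers together. That matters here, because about 47 of 83 patients (83 − 36) had no opportunity to complete 52 weeks. If the row leaves out the last on-schedule sample, it describes an earlier stage of exposure than its label suggests. The rule also says investigational product, although the trial has two, one SC and one oral. Two programmers could therefore derive different endpoints from the same text.

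**Working it through.** The SAP gives no figure to reproduce. The check is day arithmetic, with target day = 7 × week + 1. This matches the flow chart at every on-treatment visit (for example Week 40 = 281 and Week 52 = 365).

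**Completer, last dose read as the SC dose**

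- Last SC dose: 7 × 50 + 1 = Day 351; with the ±3-day dosing window (Protocol 8.1.1), Days 348 to 354.
- EOT: Day 365 ± 3, so Days 362 to 368.
- Gap from last SC dose to EOT: 365 − 351 = 14 days; shortest 362 − 354 = 8, longest 368 − 348 = 20. It is always positive, so the EOT sample is ineligible.
- Last scheduled sample before the last dose: Week 40, Day 281 ± 3. Gap: 351 − 281 = 70 days; range 348 − 284 = 64 to 354 − 278 = 76.
- Injections after the Week 40 pre-dose sample: Weeks 40, 42, 44, 46, 48 and 50, which is six including the last.

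**Completer, last dose read as any IMP**

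Protocol Appendix B gives the last week of oral dosing for each starting dose; last oral day = 7 × (last row + 1).

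| Starting dose (mg) | Last row (week) | Last oral day | EOT days (362–368) that qualify |
|---|---|---|---|
| 60 | 51 | 364 | 362, 363, 364 |
| 50 | 50 | 357 | none |
| 40 | 49 | 350 | none |
| 35 | 48 | 343 | none |
| 30 | 47 | 336 | none |
| 25 | 46 | 329 | none |
| 20 | 45 | 322 | none |

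This reading rescues only a 60 mg starter sampled on Days 362 to 364.

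**Other SAP text**

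SAP 2.5.5 mentions a last on-treatment value but does not define it. If it means the treatment epoch of SAP 2.1.4 (last SC dose + 13 days), the nominal end is 351 + 13 = Day 364, one day before nominal EOT.

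**Early stopper, worked example**

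Suppose Week 24 chemistry on Day 169, last SC dose on Day 197 and EOT chemistry on Day 211.

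- Endpoint: the closest value before Day 197 is Day 169. Day 211 is excluded.
- By-visit table: in SAP Appendix H, Schedule E, the Week 24 window is Days 127 to 224, so both samples fall in it. Distances from target are 0 and 211 − 169 = 42 days. Day 169 is kept.
- The EOT chemistry therefore enters neither the by-visit mean nor the endpoint row.

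If the Week 24 and Week 40 visits were on target, an EOT sample loses its place on Days 170 to 224 (55 days) and Days 282 to 322 (41 days). That is 96 of the 195 days from 170 to 364. This counts calendar days, not patients; the documents do not show how many patients are affected.

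**The case against.** The strongest reply is that the consequence is small and the text less absolute than it looks. Most of this stands, and it rules out several stronger readings that a reader might infer.

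- **The EOT sample can never count.** Not supported. The rule does not limit investigational product to the SC product, and a 60 mg starter can qualify through the oral product. Protocol 10.4.4 places a premature EOT visit at the time of discontinuation where possible, so a same-day sample is not excluded. The flow chart also marks IMP administration at Visit 12, in tension with footnote c.
- **The endpoint is always Week 40.** Not supported. An unscheduled or repeat sample between Week 40 and the last dose would replace it.
- **The rule governs vital signs.** This is an inference. The rule is worded for central laboratory or reading values; SAP 2.4.5.4 uses the term with no definition of its own. Interim visits could also supply later vital signs.
- **Neutrophil, platelet, ALT or LDL effects would be misreported, or values that led to stopping would be lost.** Not supported. Values after the last dose, including those drawn while a dose is withheld, still enter the PCSA counts over the TEAE period (last SC dose + 60 days), the shift tables, time-to-onset curves, worst grades, peak ALT and bilirubin plots, and listings. A completer's Week 52 value also keeps its by-visit row (window from Day 323).
- **All 47 patients lose a value.** Not supported. That figure counts patients who could not reach Week 52. An early EOT chemistry sample on Days 225 to 280 can fill the Week 40 row, and Day 211 vital signs map to Week 32 under Schedule A.

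It can also be said that tying the endpoint to the last dose is a legitimate choice. It is, but this schedule has no sample at that point, so the rule reaches back about ten weeks when a value two weeks later is available.

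**Conclusion.** The point holds in limited form. For an on-schedule completer, with the SC product as the reference dose and no unscheduled sample in between, the laboratory endpoint is the Week 40 value, 70 days (64 to 76) before the last dose. The Week 52 sample, 14 days (8 to 20) after it, is left out. At most about 36 of 83 patients could be completers. For early stoppers whose EOT visit follows the last dose, the EOT value is left out of the endpoint and, when it shares a window with an on-target visit, out of the by-visit means as well.

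The damage is confined to the endpoint row and, for some early stoppers, the by-visit means. Both are descriptive, and no safety hypothesis test depends on them. It is still worth correcting: the stated rule gives a less informative row than the data allow, and it can be programmed in more than one way.

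**What to change.** In SAP 2.4.5:

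1. Define the endpoint as the last evaluable scheduled or unscheduled value after the first SC dose through the EOT visit. Alternatively, take it through a stated window after the last SC dose that covers the 20-day maximum, for example 21 days.
2. Name the SC IMP as the reference dose.
3. State that the same definition applies to the vital-sign endpoint in SAP 2.4.5.4.
4. Show the premature EOT value as its own row in the by-visit summaries.

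Separately, reconcile the Visit 12 IMP-administration mark in the flow chart with footnote c.

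The cost is a few lines of text and a small programming change, with no new data. There is a modest downside: the endpoint may then include values up to about three weeks after the last dose. Protocol 10.4.1 treats an interruption as permanent only beyond 31 days, so values late in a long interruption could still fall outside a 21-day window. Running the definition through the EOT visit avoids a fixed cut-off.
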